Study drug will need to be prepared for infusion by the study staff in the ICU. A detailed instruction is described in the pharmacy manual. The pH of the solution for injection is around 10 and there is a minor risk for irritation at the infusion site. Based on the results of the phase 1 study in healthy subjects it was determined that administration via a central line is allowed, but not required. The study drug can also be infused in a peripheral line on the forearm. The chosen peripheral line has to be reserved for study drug administration to avoid physicochemical interaction. If subjects have a central line this can be used for administration of study drug provided that 1 of the lumina is reserved for study drug in order to avoid physicochemical interactions.

After surgery, UO will be monitored, safety assessments will be done and laboratory tests (including NC, serum creatinine (SCr; cystatin-C and other biomarkers) will be performed as per the Schedule of Assessments [[Table 1](#)].

#### Visit 3, 4 and 5

It is expected that the subject will leave the ICU within 12 to 48 hours after surgery, but will remain in the hospital. Drug administration may be done via a central line in the ICU; however, this central line may have to be removed when the subject leaves the ICU. In this case, the study drug can also be infused in a peripheral line on the forearm. The chosen peripheral line has to be reserved for study drug administration to avoid physicochemical interaction. Please note that blood samples for pharmacokinetic measurements should be taken from a different location than the location of the peripheral intravenous device used for drug administration. A detailed instruction on drug preparation and administration is described in the pharmacy manual.

If the first dose of IP administration is completed within 8 hours after T0, the second dose of IP will be administered at 24 hours after T0 and the third dose of IP will be administered at 48 hours after T0. If the first dose of IP administration is completed past 8 hours after T0, the second dose of IP will be administered at 16 hours after the start of the first dose, and the third dose of IP will be administered at 40 hours after the start of the first dose of IP.

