- Immunocompromised: the subject has received therapy that suppresses resistance to infection (e.g., immunosuppression, chemotherapy, radiation, long term or recent high dose steroids) or has a disease that is sufficiently advanced to suppress resistance to infection (e.g., leukemia, lymphoma or acquired immunodeficiency syndrome).

The APACHE-II score will be measured on visit 2 preoperatively and postoperatively during the time of drug administration at visits 2, 3 and 4, and at day 4 (visit 5) if the subject is still on the ICU. Results from local laboratory testing can be used and the results closest to the indicated time points should be recorded in the eCRF.

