10. The first dose of investigational product (IP)/study drug to be administered as soon as possible after the NC AKIRisk score is assessed between 2 and 22 hours after T0 is  $> 0.3$  (ng/mL) $^2/1000$  to allow completion of first treatment within 24 hours after T0. If the first dose of IP administration is completed within 8 hours after T0, the second dose of IP will be administered at 24 hours after T0 and the third dose of IP will be administered at 48 hours after T0. If the first dose of IP administration is completed past 8 hours after T0, the second dose of IP will be administered at 16 hours after the start of the first dose, and the third dose of IP will be administered at 40 hours after the start of the first dose of IP.  
Second and third dosing of the IP: a 2-hour treatment window before or after designated administration time is allowed.
11. Additional urine samples will be taken and stored to assess various clinical and compound related biomarkers.
12. AE will be collected from informed consent until visit 9 or until the subject is determined to be a screen failure. If the subject is discontinued from the study prior to visit 9, AEs will be collected until the EoS visit has been completed. After the end of all the procedures of visit 9 until visit 10, only serious AEs will be collected.
13. Assess data on renal replacement therapy, mortality, ICU stay, total hospital stay and duration of mechanical ventilation (time ventilation weaning, i.e., time from T0 to extubation).

*Footnotes continued on next page*

14. APACHE-II score is recorded on visit 2 preoperatively, postoperatively and during the time of drug administration at visits 2, 3 and 4 and at day 4 (visit 5) if the subject is still in the ICU. Results from local laboratory testing can be used, and the result closest to the indicated time points should be recorded.
15. Blood samples for pharmacokinetics will be collected at predose, at end of infusion and twice after study drug administration at 2 to 4 hours postdose and at 4 to 12 hours postdose of first administration, at end of infusion of second administration, and at predose and at end of infusion of third administration.
16. Blood samples for gene expression measurements will be collected at predose and 2 to 4 hours postdose of first and third administrations.

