## **6 ANALYSIS VARIABLES**

The value at presurgery will be used as the baseline unless otherwise specified for each endpoint. In case of missing value at presurgery, the last measurement before surgery will be used as the baseline.

The eGFR(SCr) will be calculated using the GFR estimation equation (2009 CKD-EPI creatinine equation) [KDIGO, 2013]. The subject's age at visit 1 should be used for calculation in this study.

Gender	Serum Creatinine	Equation for Estimating GFR
Female	$\leq 0.7 \text{ mg/dl} (\leq 62 \text{ } \mu\text{mol/l})$	$144 \times (\text{SCr}/0.7)^{-0.329} \times 0.993^{\text{Age}} [\times 1.159 \text{ if black}]$
Female	$> 0.7 \text{ mg/dl} (> 62 \text{ } \mu\text{mol/l})$	$144 \times (\text{SCr}/0.7)^{-1.209} \times 0.993^{\text{Age}} [\times 1.159 \text{ if black}]$
Male	$\leq 0.9 \text{ mg/dl} (\leq 80 \text{ } \mu\text{mol/l})$	$141 \times (\text{SCr}/0.9)^{-0.411} \times 0.993^{\text{Age}} [\times 1.159 \text{ if black}]$
Male	$> 0.9 \text{ mg/dl} (> 80 \text{ } \mu\text{mol/l})$	$141 \times (\text{SCr}/0.9)^{-1.209} \times 0.993^{\text{Age}} [\times 1.159 \text{ if black}]$

GFR: glomerular filtration rate; SCr: serum creatinine

Reference: KDIGO 2012 Clinical Practice Guideline for the Evaluation and Management of Chronic Kidney Disease. Official Journal of the International Society of Nephrology: Kidney International Supplements. 2013;3(1):1-150.

The eGFR(serum cystatin C [SCysC]) will be calculated using the GFR estimation equation (2012 CKD-EPI cystatin C equation) [KDIGO, 2013]. The subject's age at visit 1 should be used for calculation in this study.

Gender	Serum Creatinine	Equation for Estimating GFR
Female	$\leq 0.8 \text{ mg/dl}$	$133 \times (\text{SCysC}/0.8)^{-0.499} \times 0.996^{\text{Age}} \times 0.932$
Female	$> 0.8 \text{ mg/dl}$	$133 \times (\text{SCysC}/0.8)^{-1.328} \times 0.996^{\text{Age}} \times 0.932$
Male	$\leq 0.8 \text{ mg/dl}$	$133 \times (\text{SCysC}/0.8)^{-0.499} \times 0.996^{\text{Age}}$
Male	$> 0.8 \text{ mg/dl}$	$133 \times (\text{SCysC}/0.8)^{-1.328} \times 0.996^{\text{Age}}$

GFR: glomerular filtration rate; SCysC: serum cystatin C

Reference: KDIGO 2012 Clinical Practice Guideline for the Evaluation and Management of Chronic Kidney Disease. Official Journal of the International Society of Nephrology: Kidney International Supplements. 2013;3(1):1-150.

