  - At least one of eGFR based on cystatin-C equation within 7 days after T0  $\leq$  50% of the baseline value.

26. Proportion of subjects that have a reduction of NC AKIRisk score 24 hours after T0 (visit 3) to or below  $0.3 \text{ (ng/ml)}^2/1000$

27. Proportion of subjects with renal recovery, defined as a SCr value at hospital discharge equal to or lower than that at baseline

- SCr value at hospital discharge is defined as follows;

- If the hospital discharge is at or before day 7, the value at Visit 8 will be used.
- If the hospital discharge is after day 7, the value recorded as unscheduled event with check of “Last SCr value before hospital discharge.” will be used.

28. Time to ventilator weaning, defined as the time from T0 to extubation (i.e., removal of the endotracheal ventilation tube)

- Time to ventilator weaning is defined as: (Date and time of Extubation for the first record in “Mechanical Ventilation” form in eCRF – Date and time of T0) in hours.

29. Acute physiology and chronic health evaluation II (APACHE-II) up to day 4 (if the subject is on the ICU)

30. Number of readmissions to ICU

31. Number of readmissions to hospital

- All readmissions after initial hospitalization are included. Initial hospitalization is a hospitalization which includes the day of surgery
- If the date of admission of a hospitalization record is the same as the date of discharge of the previous record, then the two records will be combined into one record.

32. Changes from baseline in SCr, S-cystatin-C, eGFR based on SCr and Cystatin-C, and other biomarkers in blood and urine through 72 hours after T0

33. Area under the curve of SCr and S-cystatin-C through 72 hours after T0 (AUCSCr72h and AUCSCysC72h)

- AUCSCr72h is defined by Linear Trapezoidal Method as below;  
$$\text{AUCSCr72h (mg/dL*day)} = \text{sum of } (SCr_i + SCr_{i+1}) \times (Time_{i+1} - Time_i) / 2$$
where i=Visit 2 to 4
- AUCSCysC72h is defined in the same way as above.
- In the case of missing at 72 hours after T0, the missing value will be imputed from the last available value using Last Observation Carried Forward.

34. Area under the curve of SCr and S-cystatin-C through day 7 after T0(AUCSCr7d and AUCSCysC7d)

- AUCSCr7d and AUCSCysC7d are defined based on all available values through day 7 after T0 in the same way as AUCSCr72h and AUCSCysC72h

35. 5-level European Quality of Life 5 Dimensions Questionnaire (EQ-5D-5L) on baseline, visit 8, day 30 and day 90

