#### 7.4.4 Analysis of Exploratory Endpoints

[Analysis population: FAS, Analysis group: Randomization Arm]

The following analysis will be conducted for endpoint group 1.

- The proportion of subjects who meet the criteria will be analyzed using the CMH test with strata to control for baseline eGFR ( $< 45$ ,  $\geq 45$ ).
- The MH estimate of the adjusted common risk ratio and 2-sided 90% confidence interval will be calculated.
- If the proportion of subjects with baseline eGFR based on Serum Creatinine  $< 45$  mL/min per 1.73 m^2 for FAS is less than 10%, the above stratified analyses of CMH test and MH estimate of adjusted common risk ratio will be replaced with unstratified analyses of chi-square test and unadjusted risk ratio.

Group 1:

- All-cause mortality at day 30 (Visit 9)
- All-cause mortality at day 90 (Visit 10)
- Number of subjects needing RRT at day 30 (Visit 9)
- Number of subjects needing RRT at day 90 (Visit 10)
- Number of subjects with  $\geq 25\%$  sustained reduction in eGFR based on SCr at day 30 (Visit 9)
- Number of subjects with  $\geq 25\%$  sustained reduction in eGFR based on SCr at day 90 (Visit 10)
- MAKE30 with eGFR based on cystatin-C
- MAKE90 with eGFR based on cystatin-C
- Number of subjects with  $\geq 25\%$  sustained reduction in eGFR based on cystatin-C at day 30 (Visit 9)
- Number of subjects with  $\geq 25\%$  sustained reduction in eGFR based on cystatin-C at day 90 (Visit 10)
- Alternative derivations of proportion of subjects developing AKI using different definitions [[Table 3](#)] within 72 hours after T0. The stages will be used for subject developing AKI-SCr72h.
  - All stages AKI-UO (AKI-UO stage 2 or stage 3)
  - AKI-UO stage 3
  - AKI-SCr stage 2 or 3
  - AKI-SCr stage 2 or 3 and/or AKI-UO stage 3
  - AKI based on Cystatin-C, defined as an increase of  $\geq 10\%$  of baseline serum cystatin-C [[KDIGO, 2012](#)]

- Alternative derivations of proportion of subjects developing AKI using different definitions within 7 days after T0.
- AKI-SCr5d
- AKI-KDIGO5d
- Proportion of subjects with AKI as defined by a 50% or higher reduction in eGFR based on the Cystatin-C equation within 72 hours after T0.
- Proportion of subjects with AKI as defined by a 50% or higher reduction in eGFR based on the Cystatin-C equation within 7 days after T0.
- Proportion of subjects that have a reduction of NC AKIRisk score 24 hours after T0 (visit 3) to or below  $0.3 \text{ (ng/ml)}^2/1000$

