- Mean difference between treatment groups for change from baseline and its 90% CI will be calculated at each visit and t-test will be conducted.
- Mean (+/- SD) plot for the variables and change from baseline will be produced.

Group 5:

- APACHE-II
- SCr, Cystatin-C, eGFR based on SCr and Cystatin-C, kidney injury molecule-1 (KIM1) and AKIRisk Score (For AKIRisk Score, postsurgery value will be used as baseline. If AKIRisk Score at postsurgery is recorded several times in eCRF, the last score will be used as the value at postsurgery.)

The following analysis will be conducted for endpoint group 6.

- Descriptive statistics for the variables will be presented.
- Mean difference between treatment groups for the variables and its 90% CI will be calculated and t-test will be conducted.

Group 6:

- AUCSCr72h
- AUCSCysC72h
- AUCSCr7d
- AUCSCysC7d

The following analysis will be conducted for other endpoints.

- EQ-5D-5L
  - Descriptive statistics for the EQ-5D-5L VAS score and changes from baseline at each visit will be presented for each treatment group. In addition, the descriptive statistics will be presented by subgroups of AKI-SCr72h (Yes/No) and AKI-SCr72h stage 2 or 3 (Yes/No)
  - Mean difference between treatment groups for the EQ-5D-5L VAS and its 90% CI will be calculated and t-test will be conducted.
  - For the EQ-5D-5L qualitative domains, the number and percentage of subjects in each response level value will be reported by visit.
  - Mean (+/- SD) plot for EQ-5D-5L VAS score and change from baseline will be produced.

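### The APACHE-II t-tests compare only subjects who have a score: a post-randomisation ICU subset at visit 5, and possibly at visits 3 and 4

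*SAP*

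**What the plan says.** SAP 6.1.3 item 29 names the endpoint: "Acute physiology and chronic health evaluation II (APACHE-II) up to day 4 (if the subject is on the ICU". SAP 7.4.4 is headed "Analysis population: FAS, Analysis group: Randomization Arm" and puts APACHE-II in Group 5, where the planned inference is: "Mean difference between treatment groups for change from baseline and its 90% CI will be calculated at each visit and t-test will be conducted". SAP section 6 sets the baseline: "The value at presurgery will be used as the baseline unless otherwise specified for each endpoint". The revision history shows that the mean difference, 90% CI and t-test for APACHE-II entered in version 4.00, to give a more detailed summary. Protocol 7.4.4 names no test for APACHE-II.

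The collection rules place the ICU condition differently. SAP Table 1, footnote 14, has the score recorded "at visits 2, 3 and 4 and at day 4 (visit 5) if the subject is still in the ICU". Protocol 5.3.1.5 adds a comma that ties the condition more closely to day 4: "at visits 2, 3 and 4, and at day 4 (visit 5) if the subject is still on the ICU".

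On ICU stay, protocol 2.2.1 (Visit 3, 4 and 5) says: "It is expected that the subject will leave the ICU within 12 to 48 hours after surgery".

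No rule covers a subject who has no score because of ICU discharge or death. The missing-data sentence at the head of SAP 6.1.3 deals with event proportions. SAP 7.11.1 deals with the primary and secondary endpoints and with assay limits.

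**The concern.** Being in the ICU after the first dose is a post-randomisation state, and the SAP itself treats ICU days as an efficacy outcome (Group 2). A t-test among those still there conditions on something the drug may change. Subjects who recovered and left, and subjects who died, leave the comparison without being scored, and the two remaining groups need not be alike.

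The FAS heading makes the result look like a randomised comparison. In a proof-of-concept trial whose exploratory results may shape later studies, a small p-value for higher severity on the drug, or a missed benefit, could mislead.

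**Working it through.** The documents state no figure for APACHE-II, so there is none to reproduce. The check has two parts.

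**1. Which visits are restricted**

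| Visit | Time | Item 29 (endpoint) | Footnote 14 and protocol 5.3.1.5 (collection) |
|---|---|---|---|
| 3 | T0 + 24 h | ICU only | can be read as all subjects |
| 4 | T0 + 48 h | ICU only | can be read as all subjects |
| 5 | T0 + 72 h | ICU only | ICU only |

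Visit 5 is restricted under every reading. With ICU exit expected by 48 hours, it should hold a minority of subjects. Visits 3 and 4 are restricted only if item 29 governs.

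**2. Size of the selection effect**

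Inputs from the documents: 110 per arm and a two-sided 0.10 test. Assumed inputs:
- The score change is normal with SD 1 and has mean 0 on placebo and −d on the drug.
- A discharge driver has correlation ρ with the score change. A subject is in the ICU while the driver exceeds a threshold.
- Placebo ICU occupancy is 20% to 50%, and ρ is 0 to 1.0.

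Write c0 and c1 for the standardised thresholds in the placebo and drug arms, and λ(c) = φ(c) / (1 − Φ(c)). The ICU-only difference is

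D = −d + ρ [λ(c1) − λ(c0)].

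*(a) True benefit, d = 0.30.* If the drug moves the discharge driver by the full 0.30 SD:
- Placebo occupancy 50%: λ goes from 0.798 to 0.998. At ρ = 0.7, D = −0.30 + 0.7 × 0.200 = −0.16. At ρ = 1.0, D = −0.10.
- Placebo occupancy 20%: λ goes from 1.400 to 1.640. At ρ = 0.7, D = −0.30 + 0.7 × 0.240 = −0.13. At ρ = 1.0, D = −0.06.

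If discharge changes only through the score, the driver moves by ρ × 0.30. At ρ = 0.3 and 50% occupancy, λ goes from 0.798 to 0.856 and D = −0.30 + 0.3 × 0.058 = −0.28. At 20% occupancy D is also −0.28.

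The benefit therefore shrinks to between −0.06 and −0.28 SD and keeps its sign.

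*(b) No effect on the score, faster exit only, d = 0.* D = ρ [λ(c1) − λ(c0)]. The bracket is 1.058 − 0.798 = 0.260 when occupancy falls from 50% to 35%, and 1.400 − 1.159 = 0.241 when it falls from 30% to 20%. Rejection rates are from simulation.

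| ρ | D, 50% to 35% | D, 30% to 20% | Rejection (nominal 10%) |
|---|---|---|---|
| 0 | 0 | 0 | 10% |
| 0.3 | +0.08 | +0.07 | about 11–12% |
| 0.7 | +0.18 | +0.17 | about 19–28% |
| 1.0 | +0.26 | +0.24 | about 54–67% |

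*(c) Benefit that misses the sickest.* Suppose the drug gives 0.5 SD to all but the sickest 10%, discharge follows the score exactly, and placebo occupancy is 20% to 30%. The whole-arm effect is −0.45 SD, but the ICU-only difference is +0.21 to +0.36 SD. At 50% occupancy it is about 0.

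The model works directly on the change score and does not model the presurgery baseline separately.

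**The case against.** The strongest reply has four parts.

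- **Visits.** A reader might infer that every post-surgery APACHE-II comparison is confined to ICU patients. The documents do not establish that, because both collection rules can be read as attaching the condition to day 4 alone. This stands. Only visit 5 is certain, and the inconsistency is itself a defect to repair.
- **Direction.** A reader might infer that an effective drug will look ineffective or harmful. This is not supported. Under a uniform benefit the sign stays right. Apparent harm needs earlier exit of the less sick without a matching change in score, or a benefit that misses the sickest. The bias vanishes if discharge is unrelated to the score, though that is unlikely for a severity score.
- **Remedy.** A whole-FAS rank test (out of the ICU alive best, then by score, death worst) is not clearly better. For a 0.30 SD benefit with placebo occupancy of 50% and 20%, the ICU-only t-test has 44% and 22% power at ρ = 0.3, against 27% and 16% for the rank test. Here discharge changes only through the score. At ρ = 0.7 the order reverses: 34% and 18% against 47% and 31%. The rank test is also a different endpoint, and it would overwrite real scores at visits 3 and 4 if scores are collected there from everyone. This stands, so the rank test can only be optional.
- **Impact.** ICU days, ICU readmissions, ventilator weaning and mortality are already compared on the FAS, and the descriptive tables give n per visit. This limits the harm. It does not make the visit-5 t-test a randomised comparison, and n alone does not separate discharge from death.

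**Conclusion.** The point holds at visit 5, and at visits 3 and 4 if item 29 governs. There the SAP plans a 90% CI and t-test on a post-randomisation subset, with no rule for those who left the ICU or died. The result can be attenuated or show false harm if treatment changes ICU stay and discharge depends on severity.

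Under the assumed inputs, a 0.30 SD benefit is seen as about 0.06 to 0.28 SD. A drug that only speeds exit looks worse by about 0.07 to 0.26 SD, with rejection in about 12% to 67% of trials instead of 10%. These ranges are wide because SD, occupancy and correlation are all assumed. They show what can happen and do not predict what will.

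Nothing here supports the inference that the trial's main conclusions are at risk. APACHE-II is one of 35 exploratory items and plays no part in the primary, secondary or futility decisions.

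**What to change.** 1. Reconcile SAP 6.1.3 item 29 with SAP Table 1 footnote 14, the matching footnote to protocol Table 1, and protocol 5.3.1.5, and state at which visits the ICU condition applies.
2. At each of those visits, report APACHE-II descriptively, with the numbers in the ICU, discharged alive from it and dead by arm, and drop the CI and t-test.
3. Optionally, add a supplementary Wilcoxon test on the whole FAS at those visits, ranking out of the ICU alive best, then ICU subjects by score, then death worst. Label it as a different endpoint that is partly driven by ICU exit.

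Steps 1 and 2 need a change of SAP wording (and of the protocol text if that is the passage to be changed) and one extra table row per visit. ICU stay and mortality are already collected (SAP Table 1, footnote 13). Step 3 needs one derived variable. What is lost is a p-value that randomisation does not protect.

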#### **5.3.1.4 Quality of Life**

The EQ-5D-5L is an international standardized non-disease specific (i.e., generic) instrument for describing and valuing health status. It is a multidimensional measure of health-related quality of life, capable of being expressed as a single index value and specifically designed to complement other health status measures [EuroQol Group, 1990; Herdman et al, 2011].

The EQ-5D-5L has 5 dimensions: Mobility, Self-Care, Usual Activities, Pain/Discomfort and Anxiety/Depression. Each dimension has 5 response levels (e.g., no problems, slight problems, moderate problems, severe problems and extreme problems/unable to perform the activity). In addition, it has a visual analogue scale that elicits a self-rating by the respondent of his/her health status.

The EQ-5D-5L will be completed at or after visit 1 up to visit 2 (presurgery), at visit 8 (day 7 or hospital discharge), at visit 9 (day 30) and at visit 10 (day 90).

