## **7 STATISTICAL METHODOLOGY**

### **7.1 General Considerations**

- For continuous variables, descriptive statistics will include the number of subjects (n), mean, standard deviation (SD), median, minimum and maximum. The number of digits to be used for the mean, standard deviation and median will be added one more digit to raw data with rounding off. The minimum and maximum will be presented with the same number of digit(s) as raw data. In addition, for pharmacokinetics (PK) variables, the coefficient of variation (CV) and the geometric mean will also be calculated.

Frequencies and percentages will be displayed for categorical data. Percentages by categories will be based on the number of subjects with no missing data, i.e. will add up to 100%. Frequencies and percentages will be rounded to one decimal place. For time-to-event variables, the number and percentage of subjects with the event using Kaplan-Meier method, the cumulative event rate will be estimated and a plot will be constructed.

- Summaries based on FAS and PPS (e.g. disposition, baseline and efficacy data) will be presented by planned randomization arm, unless specifically stated otherwise. Safety analysis and other summaries based on SAF will be presented by actual treatment received. Analysis of Observational Cohort based on PFAS will be presented by prognostic factor analysis arm.
- All statistical comparisons will be made using two sided tests at the  $\alpha=0.10$  significance level unless specifically stated otherwise. All null hypotheses will be of no treatment difference, all alternative hypotheses will be two-sided, unless specifically stated otherwise.
- All data processing, summarization, and analyses will be performed using SAS® Version 9.4 or higher on Red Hat Enterprise Linux. Specifications for Table, Figures, and Listings can be found in the TLF specifications for this study.
- For continuous variables that are recorded as “ $<X$ ”, “ $\leq X$ ”, “ $>X$ ”, or “ $\geq X$ ”, the value of “ $X$ ” will be used in the calculation of summary statistics if otherwise noted. The original values will be used for the listings.
- MedDRA will be used as the coding dictionary for adverse event and medical history.
- WHODrug Global B3 will be used as the coding dictionary for previous and concomitant medication.
- For the definition of subgroups of interest please refer to [Section [7.8](#)].

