		
 
• Add the analyses of area under the curve of SCr and S-cystatin-C through 72 hours after T0 (AUCSCr72h and AUCSCysC72h)
 
	To assess the endpoint
		
 
• Clarify the definition of surgery type (lower risk surgery and higher risk surgery)
 
	For clarification
		
 
• Add frequency table of protocol version number at enrollment vs the time of first study drug taken and those subgroups
 
	To assess the impact of the protocol amendment at Ver.2.0
		
 
• Add the analyses of each individual outcomes of MAKE30/90
 
	To assess the endpoint
		
 
• Add the definition of censored subjects for time to AKI-SCr
 
	To deal with censored subjects
		
 
• Add the analyses of mean difference with 90% CI and t-test for APACHE-II, SCr, Cystatin-C, eGFR based on SCr and Cystatin-C, kidney injury molecule-1 (KIM1) and AKIRisk Score
 
	For detailed summarization
		
 
• Add the subgroup analysis of EQ-5D-5L
 
• Add the analysis of mean difference with 90% CI and t-test for EQ-5D-5L
 
	For detailed summarization

Version	Date	Changes	Comment/rationale for change
		

• Add the analysis of TEAE table by PT only

	For summarization
		

• Add summary statistics of coefficient of variation, Q1 and Q3 for the pharmacodynamic variables

	For detailed summarization
		

• Add the following analyses for Observational Cohort: Each stage of AKI-SCr72h and AKI-SCr7d, Each individual outcomes of MAKE30/90, and Association between MAKE30/90 vs AKI-SCr72h, AKI-SCr7d, and AKI-SCr stage 2 or 3

	For detailed summarization
		

• Add the data handling of the visit windows for the pharmacodynamic variables

	To exclude the values out of the visit window from the analysis

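### The exploratory EQ-5D-5L VAS comparison is a t-test with no baseline term and no named visit; adjusting for the presurgery VAS already collected would give a narrower interval

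*SAP*

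**What the plan says.** Protocol 5.3.1.4 sets the first assessment: "The EQ-5D-5L will be completed at or after visit 1 up to visit 2 (presurgery"). Randomization follows surgery, so this value comes before treatment assignment. SAP 6.1.3 lists the endpoint as exploratory: "5-level European Quality of Life 5 Dimensions Questionnaire (EQ-5D-5L) on baseline, visit 8, day 30 and day 90". SAP 6 defines the baseline: "The value at presurgery will be used as the baseline unless otherwise specified for each endpoint". If that value is missing, the last measurement before surgery is used.

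In SAP 7.4.4 the baseline VAS enters a descriptive line: "Descriptive statistics for the EQ-5D-5L VAS score and changes from baseline at each visit will be presented for each treatment group". It also enters the change-from-baseline plots. The comparison between arms is a separate line: "Mean difference between treatment groups for the EQ-5D-5L VAS and its 90% CI will be calculated and t-test will be conducted". That line contains no covariate, no mention of change and no visit. For the Group 5 variables the same section is explicit: "Mean difference between treatment groups for change from baseline and its 90% CI will be calculated at each visit and t-test will be conducted".

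SAP 7.1 sets the sidedness ("All statistical comparisons will be made using two sided tests") at alpha 0.10, which matches the 90% CI. The revision history in SAP 8 shows that the VAS test came in with version 4.00, dated 13-JAN-2022: "Add the analysis of mean difference with 90% CI and t-test for EQ-5D-5L". Neither the protocol nor the SAP contains a baseline-adjusted model for the VAS.

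**The concern.** A subject's presurgery VAS is likely to predict the later VAS to some degree. It is measured before randomization, so adjusting for it introduces no bias and removes outcome variance that has nothing to do with treatment. The planned comparison leaves that variance in. The cost is a wider 90% CI for the quality-of-life difference than the collected data would support. A chance difference in presurgery VAS between the arms also carries partly into a raw-score estimate.

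The sentence is incomplete as well. Visit 8 falls 4 to 7 days after open-chest surgery, and day 30 and day 90 come later. A mean difference with no visit attached does not say which comparison is meant.

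**Working it through.** **No plan figure for the VAS.** Neither document gives a standard deviation, effect size, correlation or power for the VAS. The only power figure is 80% for AKI-SCr72h (SAP 4). It reproduces: 110 per arm less 10% drop-out is 110 x 0.9 = 99 per arm. With 60% against 0.7 x 60% = 42% and one-sided 0.05, power is 81.7%. I use 99 per arm below as an illustrative evaluable number for the VAS.

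**Formulas.** Let rho be the correlation between presurgery and follow-up VAS, with equal SDs at both times. In squared SD units, with n per arm and large samples, the variance of the treatment difference is:

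- raw-score t-test: 2/n
- change-score t-test: 2(1-rho) x 2/n
- ANCOVA on presurgery VAS: (1-rho^2) x 2/n

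ANCOVA against raw score is therefore 1-rho^2. ANCOVA against change is (1-rho^2)/[2(1-rho)] = (1+rho)/2. Both ratios equal 0.75 at rho = 0.5.

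**Numbers, n = 99 per arm, rho assumed.** The raw-score SE is sqrt(2/99) = 0.1421 SD, so the 90% half-width is 1.645 x 0.1421 = 0.2338 SD. The last column starts from a hypothetical 80% power at two-sided 0.10: the standardized effect is 1.645 + 0.842 = 2.487, and adjusted power is Phi(2.487/sqrt(1-rho^2) - 1.645).

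| rho | SE change | SE ANCOVA | ANCOVA half-width | Narrower than raw | 80% becomes |
|---|---|---|---|---|---|
| 0.2 | 0.1798 | 0.1393 | 0.2291 | 2.0% | 81.4% |
| 0.3 | 0.1682 | 0.1356 | 0.2230 | 4.6% | 83.2% |
| 0.4 | 0.1557 | 0.1303 | 0.2143 | 8.3% | 85.7% |
| 0.5 | 0.1421 | 0.1231 | 0.2025 | 13.4% | 89.0% |
| 0.6 | 0.1271 | 0.1137 | 0.1870 | 20.0% | 92.8% |
| 0.7 | 0.1101 | 0.1015 | 0.1670 | 28.6% | 96.7% |

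At rho = 0 there is no gain over the raw-score test. At rho = 0.5 the gain over it equals having 99/0.75 = 132 subjects per arm.

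**Simulation check** (4,000 runs, 99 per arm). SEs for raw score, change and ANCOVA were 0.142, 0.172 and 0.137 at rho 0.3; 0.142, 0.144 and 0.124 at rho 0.5; and 0.144, 0.110 and 0.103 at rho 0.7. ANCOVA was smallest each time. The change score loses to the raw score when rho is below 0.5, so reading the sentence as a test on change does not remove the point.

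**Imbalance.** At equal SDs, a chance presurgery difference enters the raw-score comparison multiplied by about rho. At rho = 0.5, a 0.2 SD imbalance shifts the estimate by about 0.5 x 0.2 = 0.1 SD, against a half-width of 0.2338 SD.

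**The case against.** The strongest reply is that nothing here is wrong. Under randomization an unadjusted t-test has the right error rate and coverage. The endpoint is exploratory. Protocol 7.4.4 plans descriptive statistics for exploratory endpoints and does not list EQ-5D-5L among those to be tested. The revision history gives detailed summarization as the reason for adding the test. No decision, alpha or sample size depends on it. Covariate-free comparisons are also the SAP's habit for continuous exploratory endpoints: the Group 5 and Group 6 t-tests have no covariate, and the Cox model has treatment alone. All of this stands and keeps the point minor. None of it removes the precision gain, and the VAS test line does not even use change from baseline, as Group 5 does.

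Three stronger readings are tempting, and the documents do not support them.

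- A reader might take it as stated that the follow-up score is tested at visit 8, day 30 and day 90. The sentence says neither. The raw-score reading is an inference from the contrast with Group 5, and the table specifications that SAP 7.1 refers to are not available here.
- A reader might suppose that a baseline imbalance passes in full into the estimate. It is scaled by about rho, and the planned baseline summaries by arm would show it.
- A reader might take 80% as the power of the VAS comparison. That figure belongs to AKI-SCr72h. From a lower start the gain in power is smaller: at rho 0.4, 30% becomes only 33.6%.

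**Conclusion.** The point holds as a low-cost improvement, not as an error. The VAS comparison is valid, but its variable and visit are under-specified, and it is less precise than a baseline-adjusted analysis of the same data under either reading. Against the raw-score test, adjustment cuts the variance by rho^2, which is 9% to 49% over the assumed range of 0.3 to 0.7. Against a change-score test the variance ratio of (1+rho)/2 is 0.65 to 0.85 over that range.

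These sizes rest on an assumed rho, one value for all visits, equal SDs and large samples. The true correlation may well differ between visit 8 and day 90. The interval and variance ratios do not depend on 99 per arm; the SEs and half-widths do. The power figures depend on the hypothetical 80% start. The primary endpoint, its test and the sample size are untouched.

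**What to change.** In SAP 7.4.4, replace the VAS t-test with an ANCOVA on the VAS score at each of visit 8, day 30 and day 90, with treatment and presurgery VAS as terms. Report the adjusted mean difference and its 90% CI. Three details belong in the same sentence or two:

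- Include the baseline creatinine-based eGFR stratum (<45, >=45) only when at least 10% of the FAS have eGFR below 45, in line with the SAP's rule for stratified analyses.
- Apply the SAP 6 baseline rule when the presurgery VAS is missing.
- State how subjects with no presurgery value at all are kept, for example by simple baseline imputation. Otherwise they would drop out of the ANCOVA although a raw-score t-test would include them.

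The cost is a short text change and a different SAS procedure, with no new data. If the SAP is already final, the analysis can be reported as a documented addition in the Clinical Study Report, as SAP 1 provides for changes.
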